2.2 Study coordination and study doctors

[name] (study doctor)

Internal Medicine I and clinical chemistry

Medical faculty of the University hospital Heidelberg

[name]

[name]

Phone: [name], fax [name]

[name] (study doctor)

Specialist for Internal Medicine

Internal Medicine I and clinical chemistry

Medical faculty of the University hospital Heidelberg

[name]

[name]

Phone: [name], fax [name]

[contact]

3. Summary

The Pilot study entitled „ Asprosin Dynamics relating to serum Glucose levels under controlled alterations“ is designed to date the asprosin kinetics at various metabolic states relating to serum glucose and the correlation between asprosin and the known glucose-regulating hormones.

Asprosin is the C-terminal cleavage product of profibrillin. This new hormone is encoded by FBN1 Gen (Amino acid residues 2732-2871, molecular weight 30 kDa), which also encodes fibrillin. The hormone was initially discovered during the analysis of the genome of patients with the extremely rare Wiedemann- Rautenstrauch - syndrome (Romere C. et al 2016 Cell). According to the data so far, asprosin is a fast- induced protein hormone that acts on the liver through cell membrane receptors, where it activates the G protein cAMP- PKA pathway, leading to a rapid release of glucose into the circulation and to compensatory insulin production. The above seems to match the constellation found in overweight type 2 diabetes patients or patients with metabolic syndrome ("insulin resistance"). Diabetic mice were able to normalize their glucose and insulin levels by asprosin-binding antibodies. According to a recent study (Romere C. et al 2016 Cell), asprosin had no influence on the serum concentration of glucagon, epinephrine, nor- epinephrine and cortisol in mice. In humans it is known that asprosin increases during fasting.

The liver- related glucose release into the blood circulation is crucial for the brain function and overall survival during fasting. In addition, a compensatory rise in asprosin is expected during a hypoglycemic episode. In this pilot study, the asprosin concentration is measured both in participants with type 1 Diabetes mellitus, with or without hypoglycemia unawareness during a hypoglycemic phase. These relevant measurements are compared in the two subgroups, consisting of 5 persons each.

By correlating asprosin values with other regulating hormones, there is hope to better understand the pathomechanism of hypoglycemia unawareness. Recently discovered is that the recombinant asprosin administration in mice allows both the blood glucose and the insulin to rise. It is therefore very likely that further studying of asprosin could provide new insights into the (patho-) physiology of the intermediary metabolism disorder.

According to the above, the following hypotheses arise:

- Asprosin, as fast- induced protein hormone, increases serum levels in type 1 diabetics with or without diabetes late- complications during a hypoglycemic phase.
- Asprosin increases serum levels more significantly in diabetics without hypoglycemia unawareness compared to diabetics with hypoglycemia unawareness.
- There is probably no correlation between asprosin and the previous known regulating hormones.

In order to investigate these hypotheses, study participants will be initially profoundly examined in our Clinical Study Center regarding both their glycemic metabolic responses and the clinical findings relating to their possible micro- and macrovascular complications. In addition to this quality of life, well-being, depression and neuropathic pain is going to be taken into account.

This is to be the first study of its kind, in which plasma levels of asprosin is determined and Type 1 diabetics with and without hypoglycemia unawareness are thoroughly examined in order to identify possible differences and similarities for the better determination of the new hormone utilizing the framework of hyperinsulinemic Clamp- Tests. The intention behind is to better understand the (patho-) physiology of the hypoglycaemia unawareness, as well as to better characterize the physiological properties of asprosin.

4. Scientific background and state of the art

The number of treated type 2 diabetic patients in Germany is an estimated 6 million (Rathmann et al. 2010). However, this number underestimates the true scale of the disease, since, as in most Western-European countries, the prevalence of undiagnosed patients is high (Rathmann et al. 2010). Epidemiologic studies undermine that type 2 diabetes according to the current definition increasingly begins in mid-adulthood (Rathmann et al. 2010). Chronic progress of the disease and the need for ongoing treatment mean a huge burden for the patients. **Especially diabetes- associated late complications cause a significant reduction in life- quality and an increase in mortality (Roglic et al. 2005) and should therefore become the target of future therapeutic efforts.** Complications manifest as macroangiopathy in the sense of coronary artery disease, peripheral artery disease, and cerebrovascular insufficiency. Moreover, as a consequence of microangiopathy, diabetic nephropathy, neuropathy, and retinopathy can occur, leading to renal insufficiency, loss of eyesight, or diabetic foot syndrome as well as the severe acute complication of hypoglycemia unawareness (Schleicher et al. 2001).

Current therapeutic strategies focus on treatment of hyperglycemia (UKPDS, ACCORD, ADVANCE etc). However, under closer observation, HbA1c and therefore glucose metabolism are insufficient surrogate markers for the development of relevant micro- and macrovascular complications. **This means, therefore, that the development of diabetes mellitus and clinically relevant complications especially the hypoglycemia unawareness are inadequately understood.**

The mechanisms leading to this disorder of glucose-insulin metabolism are still not fully clarified. The discovery of the hormone asprosin from colleagues in Houston, USA, could now help us to a new point of view concerning diabetes mellitus (Romere C. et al 2016 Cell). These American scientists originally analyzed the genome of patients with Weidemann- Rautenstrauch syndrome. This is a rare progeroid disorder, in which children appear to age rapidly. The researchers discovered through genome analysis that these patients lack an unknown hormone. They called it "asprosin", from the Greek word "aspros" meaning white.

Patients suffering with progeroid disorder lack subcutaneous white adipose tissue, resulting to lipodystrophy. Further investigations have shown that asprosin is mainly secreted by white adipose tissue, especially during fasting, before reaching the liver via blood- circulation. It there adapts itself to specified receptors and through a procedure including cAMP pathways leads to further glucose- release in the releases glucose into the blood- circulation.

People with Weidemann's Rautenstrauch syndrome exhibit particularly low insulin concentrations, apparently because of this Asprosin deficiency. It was as a result deduced that asprosin is a fasting-induced protein hormone.

The authors recognized that asprosin increases both blood glucose and insulin in mice. However, it did not affect the serum concentration of glucagon, epinephrine, norepinephrine and cortisone in mice.

People with insulin resistance show elevated asprosin levels, as the researchers of the above study noticed. If the recently discovered hormone is suitable as an alternative treatment of type 2 diabetes or a tool for insulin resistance screening awaits still to be answered, as further clinical studies are requested. Pharmacological approaches, such as specified antibodies, targeting Asprosin-inhibition, could reduce the serum glucose and improve insulin sensitivity, according to the current study. In mice with diabetes, the authors succeeded in neutralising the Asprosin's effect using recombinant antibodies, leading to serum glucose and insulin levels reduction. After an injection of recombinant Asprosin the above levels were accordingly elevated.

The situation in newly-diagnosed type 1 diabetics without insulin resistance is similarly undecided. Incidence of type 1 diabetes increases continually (Ehehalt et al. 2012), and due to manifestation earlier in life, the risk for diabetic complications and reduction in quality of life is even more pronounced.

As far as we know, the pathogenesis of type 1 diabetes is an autoimmune destruction of insulin-secreting beta-cells in the pancreas, resulting in absolute insulin deficiency. From our own studies, we know that diabetic complications can be found in rare cases of type 1 diabetics shortly after first diagnosis. As in type 2 diabetes, patients with good blood glucose control (HbA1c 6-7%) can develop diabetic complications over time, whereas some patients with insufficient blood glucose control over long time-periods never develop late diabetic complications (clinical observation). **Therefore, pathogenesis of diabetic complications does not seem to be entirely dependent on glucose metabolism.**

As a result, the only similarity between the two diabetes types seems to be the name „diabetes mellitus“, which only describes a symptom.

In addition to the aforementioned pathomechanisms in this context, in both type 1 and type 2 diabetics, polygenetic factors, environmental-, nutritional- and lifestyle factors, which are supposed to be associated with the development of diabetic complications, are being discussed. These associations with the development of diabetic complications are being examined in the

German Diabetes Study (Deutsche [name]), an ongoing multicenter observational study (in Heidelberg: ethics number **S-232/2013**).

A severe acute complication, which affects predominantly type 1 diabetics (at least a quarter of all type-1 diabetics, Gerich et al., 1991), but also type 2 diabetics with low C-peptide values, is the hypoglycemia unawareness and the associated autonomic failure ("Hypoglycemia Associated Autonomic Failure", HAAF). Reduced glucose serum concentration usually initiates a specific series of responses (Schwarz et al., 1987, Mitrakou et al., 1991, Fanelli et al. 1998). The human organism itself is protected against hypoglycaemia through a physiological mechanism involving the activation of the autonomic nervous system or hormone related counter-regulation. The function of the brain is directly dependent on the glucose supply, because it can neither accumulate it in sufficient quantities nor produce it itself. A reduced insulin release is the first step against hypoglycemia (Cryer 1997). The secretion of regulating hormones such as glucagon (stimulates hepatic glucose production), adrenaline (stimulates hepatic and renal glucose production and restricts the use of glucose by other tissues other than the brain), cortisone and growth hormone (both support glucose production) increase as soon as the glucose level is below the corresponding glycemic threshold (Cryer 1997). In healthy persons, insulin secretion is reduced by a glucose level of about 80-85 mg / dl (4.4-4.7 mmol / l). In the case of values between 65 and 70 mg / dl (3.6-3.9 mmol / l), an increased release of counter-regulatory hormones begins (Schwarz et al 1987, Mitrakou et al., 1991, Fanelli et al. 1998). Normally, most patients will be aware of the first hypoglycaemic symptoms in glucose levels between 50 and 55 mg / dl (2.8-3.1 mmol / l). Cognitive dysfunction occurs by levels below 50 mg / dl (<2.8 mmol / l). A loss of senses is usually expected only by values below 35 mg / dl (1.9 mmol / l) (Schwarz et al., 1987, Mitrakou et al., 1991). Glucose serum levels below 20 mg / dl (1.1 mmol / l) lead to cerebral seizures or coma.

To optimize therapeutic strategies and to better understand and avoid secondary diseases and acute complications such as hypoglycemia unawareness, it would possibly be of great importance to study the new hormone "asprosin". Being a fast-induced plasma glycoprotein measuring or altering Asprosin levels could further help develop individualized prevention and therapy.

In this pilot study, five people with and five without hypoglycemia unawareness will be recruited and comprehensively phenotyped. The participants will be type 1 diabetics with a BMI between 25 and 35 kg / m² and 18 to 75 years of age. An extensive phenotyping of the participants will be performed, which will bring important new data on type 1 diabetes and diabetes related late complications. What takes place is the characterizing of the participants regarding their Asprosin

levels when fasting and after glucose or insulin administration (hyperinsulinemic Clamp test) as well as of the diabetic late complications even in the subgroups that form. Eventually, the correlation of the asprosin serum concentration against the other regulating hormones such as glucagon, catecholamine and cortisol will be thoroughly evaluated. A platform for discussion is created in this way, one that can still not be reached through current studies.

This is to be the first study of its kind, in which plasma levels of asprosin is determined and Type 1 diabetics with and without hypoglycemia unawareness are thoroughly examined in order to identify possible differences and similarities for the better determination of the new hormone utilizing the framework of hyperinsulinemic Clamp- Tests. The intention behind is to better understand the (patho-) physiology of the hypoglycaemia unawareness, as well as to better characterize the physiological properties of asprosin.

5. Aims and hypotheses of the study

The following hypotheses shall be studied:

- Asprosin, as fast- induced protein hormone, increases serum levels in type 1 diabetics with or without diabetes late- complications during a hypoglycemic phase.
- Asprosin increases serum levels more significantly in diabetics without hypoglycemia unawareness compared to diabetics with hypoglycemia unawareness.
- There is probably no correlation between asprosin and the previous known regulating hormones.

In order to investigate these hypotheses, study participants will be initially profoundly examined in our Clinical Study Center regarding both their glycemic metabolic responses and the clinical findings relating to their possible micro- and macrovascular complications. In addition to this quality of life, well-being, depression and neuropathic pain is going to be taken into account.

To investigate these hypotheses, associations of „diabetic“ micro- and macrovascular complications with different metabolic pathways, especially glycolysis, insulin resistance, impairment of insulin secretion, psychosocial factors (depression, quality of life), cognitive

parameters, as well as clinical and laboratory parameters will be examined during basic testing in ten persons with diabetes type 1, five persons with and five without hypoglycemia unawareness. Asprosin levels were then determined during fasting periods as well as after glucose and insulin administration (hyperinsulinemic clamptest). The determination of glucagon, catecholamines and cortisol takes place during the execution as well as at the end of the clamp test and are being correlated to Asprosin values.

The findings may be crucial to understanding the pathophysiology of hypoglycemia unawareness and the development of further prevention methods.

Basic testing/cross-sectional analyses:

- Do the participants already manifest diabetes late complications?
- Do Asprosin serum levels increase after 12 hours of fasting in all participants? Is the fasting- Asprosin level higher in diabetics with insulin resistance compared to diabetics without insulin resistance?
- Are the Asprosin values after glucose administration in type 1 diabetics with or without hypoglycemia comparable unawareness and were they indicative of a comparable pathogenesis?
- How do Asprosin levels alter after insulin administration in the different subgroups during a phase of lower glucose serum levels (target range 60-70 mg / dl)? Could a correlation of the asprosin concentration to the known regulating hormones eventually exist?

6. Study design and examinations, Method

It is a clinical pilot study, which will be launched mono-centric. The following examinations are included in study, which are separated into different modules as presented in the following passage.

Recruitment of study participants will take place on medical wards and in outpatient facilities of the University Hospital Heidelberg. Moreover, there will be informative events at the University Hospital Heidelberg where study participation will be offered, and our press office will be informed and will release articles in the local press to raise attention to the study. According to experience, word of mouth will be spread as well. The participants will be ten persons with diabetes type 1, five persons with and five without hypoglycemia unawareness.

People interested in study participation can contact the Clinical Study Center via phone or e-mail. Written information will be sent by post or handed out directly. At a separate appointment, oral and written informed consent will be obtained by a study doctor, so that study participants have enough time to think.

Basic testing will take one day. On the first day are planned various non-invasive clinical routine examinations. Study participants will be invited between 10 and 12 a.m. starving. The basic tests take three to four hours, depending on the number of study participants invited on that day. Quantitative sensor testing takes approximately 90 minutes of additional time, it will be take place on the first day too. On a second day a hyperinsulinemic clamp examination is performed, which will be scheduled separately, within four weeks of basic testing.

The clamp lasts about 5 hours including the follow-up time. Initialy blood is drawn in order to measure of plasma glucose, Asprosin, insulin, C-peptide, adrenaline, norepinephrine, glucagon and cortisone concentrations, and twice for the biobank (at the beginning and end of the test) and for determining the values of the routine lab testing will be performed. In addition, a urine examination takes place. All tests will be performed according to SOPs by trained personnel.

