It is a standard scientific test for the determination tissue sensitivity to insulin. In this study the asprosin kinetic in various hyperglycemic and euglycemic phases as well as the correlation between asprosin levels to the other known regulating hormones (adrenaline, norepinephrine, glucagon and cortisone) will be investigated. During the hyperglycemic phase, as well as at the end of the clamp test, the mechanical pain sensitivity (MPS) and the mechanical allodynia in the case of moving stimuli (DMA) are performed on both sides of the hands and feet. This in order to determine the changes in the sensibility of the skin, the sense of pain itself and sensitivity deficits with QST in the various hyperglycemic and euglycemic phases. The implementation of the QST is described in detail in page 15 of the study protocol.

The Examination-Clamp Test starts in the morning at 07:15 after a fasting period of 12 hours. Initially blood is drawn to determine plasma glucose, insulin, C-peptide, adrenaline, nor-

adrenaline, glucagon and cortisone levels. In order to construct the biobank and for the routine lab testing, blood tests are executed both at the beginning and end of the test. In addition, urine examination is also performed.

An intravenous glucose tolerance test (ivGTT) takes place, in which 1 ml / kg of glucose 30% is as bolus injected and the serum glucose is controlled over 1 hour, initially every 2 minutes and later in gradually prolonged intervals. Additionally blood tests for insulin, C-peptide and asprosin determination are executed. This test will be used to determine the pancreatic insulin reserve and to monitor asprosin kinetics during hyperglycemia.

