6.7 Concomitant therapy

The study does not influence the study participants' regular medication of other medical treatment in any way.

7. Statistical analysis and sample size calculation

The number of 10 subjects suffices for this pilot project. The aim of the study is to assess the asprosin effect during the hyperinsulinemic clamp test as well as its correlation to the rest of

Asprosin dynamics relating to serum Glucose levels under controlled alteration from Version 1.1 Stand 31.05.17

known regulatory hormones. Because of the low number of participants, only non-parametric evaluations, as well as descriptive and graphical statements, are used. Depending on the parameter, relating or non-relating non-parametric tests are performed. It is a pilot study in which no large statistical calculations are possible or, currently necessary. No biometrics will be involved in the evaluation.

The effect variables determined in this study, in particular asprosin kinetics under different glucose related metabolism conditions, can be further used for possible power analysis of larger future studies.

8. Data collection and data management

All collected data from the study will be transferred into a case report form (CRF), which contains an unequivocal participation number. Moreover, all samples will be labeled with a code number, so that all analyzes can be performed by use of a pseudonym. Questionnaires containing personal data will be stored separately. The code can only be associated with the study participant by a small group of direct employees of the Study Center for Diabetes Research of the University of Heidelberg. Decoding only takes place in case of withdrawal from study participation in order to erase all data, or in case of severe medical findings about which the study participant has to be informed. In statistical analyses and publications, data will be completely anonymous. Anonymization will be performed during creation of excel sheets of SPSS tables, which do not contain a pseudonym anymore. All data and results from the study are subject to professional secrecy. Results in the context of medical publications will only be presented as statistical entities. Study files will be stored in a lockable room, which can only be accessed by employees of the Study Center for Diabetes Research of the University of Heidelberg. Clinical data will be stored for 15 years.

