Asprosin dynamics relating to serum Glucose levels under controlled alteration

Statistical Analysis Plan

Heidelberg, 31/05/2017

Statistical analysis and sample size calculation

The number of 10 subjects suffices for this pilot project. The aim of the study is to assess the asprosin effect during the hyperinsulinemic clamp test as well as its correlation to the rest of known regulatory hormones. Because of the low number of participants, only non-parametric evaluations, as well as descriptive and graphical statements, are used. Depending on the parameter, relating or non-relating non-parametric tests are performed. It is a pilot study in which no large statistical calculations are possible or, currently necessary. No biometrics will be involved in the evaluation. For evaluating differences in asprosin concentrations during different time points of the clamp, Wilcoxon test will be used. For correlations between asprosin concentration and blood glucose concentration, Kendall-tau test will be used. For ruling out confounders, linear regression analysis will be performed. For descriptive analysis, median and range will be given. As software, IBM SPSS 23.0 will be used.

The effect variables determined in this study, in particular asprosin kinetics under different glucose related metabolism conditions, can be further used for possible power analysis of larger future studies.

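### The protocol asks whether post-glucose asprosin is comparable in the two groups, but the SAP plans nothing that could support comparability with five against five

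*Protocol*

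**What the plan says.** The question is in protocol section 5, in the list headed basic testing/cross-sectional analyses. The word order is disturbed ("comparable unawareness and were they indicative of a comparable pathogenesis"). I read it as asking whether asprosin after glucose is comparable in participants with and without hypoglycemia unawareness, and whether that points to a shared pathogenesis. It is not one of the three hypotheses at the start of section 5.

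The groups are "five persons with and five without hypoglycemia unawareness". Section 7 gives no calculation for this size: "The number of 10 subjects suffices for this pilot project".

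The post-glucose data come from the intravenous glucose tolerance test in section 6.1, Module 3: "This test will be used to determine the pancreatic insulin reserve and to monitor asprosin kinetics during hyperglycemia". Glucose is followed for one hour. Asprosin is sampled too, but no asprosin sampling times are given and no summary of the hour is chosen for comparing the groups.

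On analysis, the SAP says "Depending on the parameter, relating or non-relating non-parametric tests are performed". The one test it names for asprosin differences is for time points: "For evaluating differences in asprosin concentrations during different time points of the clamp, Wilcoxon test will be used". Kendall's tau is assigned to asprosin against glucose, and linear regression to confounders. For description, "For descriptive analysis, median and range will be given". Graphs are also foreseen. The SAP gives no significance level, no sidedness, no definition of comparable and no interval for a difference between groups.

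**The concern.** A question about similarity needs an estimate of the difference and a statement of how large a difference the data leave open. This plan supplies neither. The group comparison can end in two ways that look like similarity: a test that does not reach significance, or ranges that overlap. With five per group, both are common when the groups truly differ.

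The protocol attaches a mechanistic inference to the answer. If either outcome were reported as comparable asprosin, a statement about shared pathogenesis could rest on lack of power.

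This question is separate from the hypothesis that asprosin does not correlate with the other regulating hormones. Care in interpreting that hypothesis would not by itself cover this one.

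**Working it through.** **Inputs from the documents.** Five per group (protocol section 5); an unpaired non-parametric test, not named (SAP). The stated total of 10 comes with no effect size, SD, significance level or power, so there is no figure to reproduce.

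**Assumptions.** Two-sided 0.05; Mann-Whitney as the unpaired test; normal data with equal SD; true differences of 0.5 to 2.0 SD.

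**Rejection region of the exact test.** There are C(10,5) = 252 equally likely rank allocations under no difference. The values U = 0, 1, 2 arise in 1, 1 and 2 of them, so P(U ≤ 2) = 4/252 = 0.0159. Two-sided, 2 × 0.0159 = 0.0317. Including U = 3 gives 0.0556, above 0.05. The exact test therefore rejects at U ≤ 2 or U ≥ 23.

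**Rejection region of the asymptotic test (no continuity correction).** z = (U − 12.5)/√(25 × 11/12) = (U − 12.5)/4.79. At U = 3, z = −1.98, beyond −1.96, so this version also rejects at U = 3. It is slightly more powerful, with attained level 0.0556.

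**Chance of a non-significant result.** The exact and asymptotic columns come from 400,000 simulated trials per difference; the t-test column comes from the noncentral t distribution with 8 degrees of freedom.

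| True difference | Exact Mann-Whitney | Asymptotic Mann-Whitney | t-test |
|---|---|---|---|
| 0.5 SD | 93% | 89% | 89% |
| 1.0 SD | 79% | 71% | 71% |
| 1.5 SD | 57% | 45% | 45% |
| 2.0 SD | 32% | 22% | 21% |

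Non-significance is the likelier result up to about 1.6 SD with the exact test. With the other two, the crossover lies between 1.2 and 1.5 SD. With a one-sided exact test at 0.05 (reject at U ≤ 4), non-significance is 60%, 34% and 14% at 1.0, 1.5 and 2.0 SD, and the crossover is about 1.2 SD.

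**Overlapping ranges.** Two groups of five have non-overlapping ranges only when U = 0 or U = 25. Both values lie inside the exact rejection region, so the ranges overlap in every trial that is non-significant by the exact test, and in some significant ones. Overlap is thus at least as frequent as the exact column and is weaker evidence of similarity.

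**What an interval would show.** The exact interval for the shift runs from the 3rd to the 23rd of the 25 ordered pairwise differences. Its confidence is 1 − 2 × 4/252 = 96.8%. In simulation its median half-width is about 1.62 SD. As a check, the expected size of a 95% t interval is 2.306 × √(2/5) = 1.46 SD either side. A typical null result would leave differences of about 1.5 SD open.

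**Would an equivalence margin help?** If the groups were identical, the exact interval would lie within ±1 SD in about 1% of trials. With two one-sided t-tests at 0.05 each, equivalence would be concluded in about 0.05%, 7%, 42% and 78% of trials for margins of 0.5, 1.0, 1.5 and 2.0 SD. Only margins too wide to mean comparable give a reasonable chance of success. For 80% power at a 1 SD margin, n per group = 2 × ((1.645 + 1.282)/1)² ≈ 17.1, so 18.

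**The case against.** Four points count against making more of this.

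First, a reader might infer that the trial will declare comparability when p > 0.05. The documents do not say so. Section 5 puts an open, two-part question, asks whether the values are indicative without asserting that they are, and sets no decision rule. This objection stands, and the point must be limited to the absence of any safeguard.

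Second, a reader might infer that the SAP contains only difference tests, so that similarity could come only from a failed one. That is too strong. Medians, ranges and plots of ten people show nearly all the data, and for n = 5 the range is itself an exact interval for a group's median with confidence 1 − 2/2⁵ = 93.75%. But it describes each group separately, not the difference between them, and overlap is a poor guide to similarity.

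Third, a reader might infer that a non-significant result is likely however far apart the groups are. The table contradicts this: at 2 SD significance is the likelier result under every test shown. At 1.5 SD the answer depends on the test, and the documents specify neither the test nor its level.

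Fourth, the limitation is largely disclosed. The SAP states "It is a pilot study in which no large statistical calculations are possible or, currently necessary" and presents the results as input to later power calculations. That lowers the weight of one exploratory question. It does not tell the analyst how to answer it.

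**Conclusion.** The point holds in a limited form and is minor. The protocol poses a similarity question with an inference to pathogenesis, and the SAP provides neither a definition of comparable nor an interval for the group difference. With five against five, non-significance would occur in about 71% to 79% of trials at a true difference of 1 SD and 45% to 57% at 1.5 SD, across the two-sided tests considered. It would not be the usual result at 2 SD. These figures rest on normal data with equal SD and a two-sided 0.05 level, none of which is in the documents. The weakness of range overlap as evidence follows from ranks alone and needs no such assumption. The documents do not support the claim that the trial will report comparability from p > 0.05; they leave that route open.

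**What to change.** In the SAP:

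- Name one post-glucose asprosin summary from the glucose tolerance test hour, for example the area under the curve or the value at a stated time, together with the asprosin sampling times it needs.
- Report the Hodges-Lehmann difference between the groups in that summary with its exact 96.8% interval.
- State that neither a non-significant difference nor overlapping ranges will be reported as comparability.

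In protocol section 5, replace the pathogenesis clause with estimation of the between-group difference in post-glucose asprosin.

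An equivalence margin is not needed. The documents give no asprosin variability from which to set one, and at this size any margin narrow enough to be meaningful would almost always return inconclusive.

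The cost is wording in both documents, with no extra participants or procedures. The downside is that the likely conclusion on this question becomes inconclusive. The interval would also serve the SAP's stated aim of informing larger studies better than median and range alone.
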